# 12.3 Planned Interim Analyses (if applicable)

Not applicable.

## 12.3.1 Safety Review

Not applicable. This is a low risk study and safety will be monitored by research team members, the PI, IRB and the CSOC. For the current study, risks from dental cleaning using SADE are similar to traditional dental visits (e.g., gingival bleeding, mild discomfort). For a full list of potential risks, see Section 2.2.1.

# 12.3.2 Efficacy Review

There are no interim analyses planned for this trial. Efficacy of the primary factor of environment will be determined as defined in the final analysis plan.

# 12.4 Final Analysis Plan

Descriptive statistics will be performed for all variables of interest to describe the participant population at baseline, including attrition rate and missing data, to compare those randomized to SADE first vs. those randomized to RDE first. We anticipate a low attrition rate (~10%) and will impute missing data for intent-to-treat analyses using Markov Chain Monte Carlo (MCMC)

imputation with multiple values imputer for each missing value averaged for an estimation for analyses. Bivariate associations between outcomes (physiological anxiety and children's negative behavioral responses), environment (SADE or RDE), and covariates (age, gender, order of visit, autism severity, IQ, and sensory sensitivity) will be described. The primary objective of determining difference between dental environments will be tested using intent-to-treat models examining the within-subject factor of dental environment (SADE vs RDE) using repeated measures ANCOVA for each outcome. *A priori* covariates include age (continuous), randomized order of visit, gender, and temperature. Other participant characteristics that are unbalanced between order of visits will be included as covariates *ad hoc*.

The secondary objective of examining the mediating effect of physiologic response on behavioral outcomes will be tested by first examining the bivariate relationships between EDA and behavioral outcomes, and then adding EDA estimates (SCL and NS-SCR) to models of dental environment difference on behavioral outcomes, and examining the change in the within group coefficients. A change in coefficient >15% will be considered evidence of mediation. While we have several outcomes, we specify only one mediator, thus we will apply a rational approach to examination of multiple outcomes, and will assess the fidelity of our study by estimating effect sizes (Cohen's d) of the dental environment before and after the mediation factors are assessed to confirm that statistical results were supported by clinical relevance of findings. If physiological anxiety does mediate the environment's effect on negative behavioral responses, we anticipate that the anticipated effect of environment will be eliminated once we add in EDA to the models specified in Hypothesis 2. Analyses will be performed using SPSS (v.22); a priori two-sided  $\square = 0.05$ .

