#### Retention

To aid in retention of study participants, a series of steps will be taken. Reminder phone calls, texts, and/or e-mails for meetings and dental visits will occur (based on stated parent preference). Additionally, the first meeting, consisting of the consent process and survey completion, will take place at the family home or CHLA, whichever is more convenient for the family. Utilizing these strategies in the R34 pilot study, we were able to retain 98% of our participants. However, since not all participants will be patients in the CHLA Dental Clinic, we expect there may be a larger loss. We have allowed for a loss of 10%, targeting a sample of 165 participants with complete data from a recruited sample of 220 children with ASD.

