# 12.2 Sample Size Considerations

The R34 pilot study provided estimates of effect size used for sample size calculations, which ranged greatly across measures for children with ASD. Figure 1 shows the N required to detect a difference between dental environments based on the results from the pilot study. As these effect sizes were typically smaller than those found by Shapiro et al., $^{50-51}$  they represent a more conservative estimate of sample size, and have the benefit of being specific to the population and measures proposed here. Sample size estimates were computed to detect the effect of the repeated measurement environment for outcomes specified in the primary objective, with EDA being the primary outcome (Hyp 1) and distress behavior, perception of pain, and sensory discomfort secondary, with 1-=0.80 and -=0.025 (Hyp 2). In the R34 pilot study, the effect sizes for EDA difference between environments ranged from Cohen's d = 0.44-0.46 (see Figure

1). The effect size of the environment difference for sensory discomfort and pain intensity were large (d's = 0.69 and 0.62, respectively), while distress behavior measure effects were small (d's ranging from 0.11 to 0.23), likely due to the restricted range of answers in those measures. Attrition in the pilot data was extremely low (2%), however the more conservative attrition estimate of 10% was used for these calculations. Thus we will recruit 220 children with ASD, anticipating having repeated measures on 165. This N will allow for the detection of a within group change attributable to environment of Cohen's d = 0.22. Figure 1 shows the estimated sample size, including the effect sizes from the R34; as indicated, our target sample size, after attrition, should have sufficient power to detect differences in our primary outcome.

[figure not shown]

Figure 1. Sample size estimates based on ASD participants of R34 Pilot and Feasibility Study

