# **Primary Objective: Hypothesis 1**

The primary objective is to test the effect of the environment (SADE vs RDE) on physiological anxiety. Hypothesis 1 specifies an effect of environment on the outcome, thus the main effect of interest will be  $B_1$ , the dental environment.

Hyp 1: EDA =  $B_0$  +  $B_1$ \*Environment + Covariates

## Secondary Objective 2: Hypothesis 2

The secondary objective explores further outcomes and mechanisms of the group differences. Hypothesis 2 is analogous to those in the primary aim and have the same coefficients of interest. However, there are multiple, secondary outcomes including behavioral distress, perception of pain, and sensory discomfort). As noted above, we will apply a rational approach to examination of multiple outcomes and will assess effect sizes of the coefficients, in addition to the statistical significance.

Hyp 2: Negative behavior =  $B_0 + B_1$ \*Environment + Covariates

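### Imputed values are averaged into one completed data set before analysis, so standard errors and p-values for the primary EDA comparison come out too small

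*Combined protocol and SAP*

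**What the plan says.** On missing data, section 12.4 (Final Analysis Plan) states: "We anticipate a low attrition rate (~10%) and will impute missing data for intent-to-treat analyses using Markov Chain Monte Carlo (MCMC"; the sentence continues "imputation with multiple values imputer for each missing value averaged for an estimation for analyses". The thing averaged is the set of values drawn for each missing value. The same paragraph tests the primary objective with "intent-to-treat models examining the within-subject factor of dental environment (SADE vs RDE) using repeated measures ANCOVA for each outcome", at a two-sided level of 0.05. Under Primary Objective: Hypothesis 1 the plan adds that "Hypothesis 1 specifies an effect of environment on the outcome, thus the main effect of interest will be" the environment coefficient in the EDA model.

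The documents do not describe analysing each completed data set separately, combining estimates or variances across imputations, the number of imputations, or a complete-case or mixed-model sensitivity analysis.

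On the amount of missing data, section 5.3 (Retention) says: "We have allowed for a loss of 10%, targeting a sample of 165 participants with complete data from a recruited sample of 220 children". Section 12.2 says: "Thus we will recruit 220 children with ASD, anticipating having repeated measures on 165". The stated loss is 10%, but 165 of 220 is a shortfall of 25%.

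**The concern.** Multiple imputation draws several values so that the spread between them can carry the uncertainty about what was not observed. Averaging the draws first removes that spread. The result is close to a regression-mean imputation: it lies near the prediction from the child's other visit, with almost no residual around it.

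In this crossover the consequence is direct. A child who misses the second cleaning supplies no observed SADE-minus-RDE contrast. The averaged value manufactures one, with much less variance than a real contrast, and the ANCOVA gives it a full degree of freedom. The standard error of the environment effect is therefore understated, confidence intervals are too narrow, and the test rejects too often. This affects the primary EDA test and each secondary ANCOVA run on the imputed data. Sections 12.4 and Hypothesis 2 also rely on Cohen's d to judge multiple outcomes. If d is standardised on the SD of the contrast, it is inflated for the same reason.

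**Working it through.** **Plan's own figure.** With 165 pairs, 80% power and two-sided 0.05, the detectable effect is (1.960 + 0.842)/√165 = 0.218, which matches the stated d = 0.22. The power case therefore rests on 165 observed contrasts. An analysis that treats 220 as observed would nominally detect 2.802/√220 = 0.189, a precision the data do not have.

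**Inputs.** From the documents: 220 children, two visits, two-sided 0.05, loss f of 2% (pilot, section 12.2), 10% (stated) or 25% (1 − 165/220). Assumed, because the documents give no figures: within-child correlation ρ of 0.3 to 0.7, normal outcomes, and second visits missing completely at random.

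**Approximation for many draws.** Take the variance of a real contrast, 2(1 − ρ)σ², as 1.

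- Contrast built from an averaged value: its variance is (1 − ρ)²σ², or (1 − ρ)/2 in relative terms. At ρ = 0.5 that is 0.25, a quarter of a real one.
- Variance the analysis reports: (1 − f) + f(1 − ρ)/2.
- True variance of the estimate: (1 + ρ)/[2(1 − f)] + (1 − ρ)/2.
- SE ratio: √(reported/true). Type I error: 2[1 − Φ(1.96 × ratio)].

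At ρ = 0.5:

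- f = 10%: reported 0.90 + 0.025 = 0.925; true 0.75/0.90 + 0.25 = 1.083; ratio √(0.925/1.083) = 0.924; type I error 2[1 − Φ(1.811)] = 0.070.
- f = 25%: reported 0.75 + 0.0625 = 0.8125; true 0.75/0.75 + 0.25 = 1.25; ratio √0.65 = 0.806; type I error 2[1 − Φ(1.580)] = 0.114.
- f = 2%: reported 0.985; true 1.015; ratio 0.985; type I error 0.054.

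**Simulation under the null.** 220 children in an AB/BA crossover, with M = 5 or 20 proper normal-regression imputations. The within-child contrast was analysed adjusting for order, with 3,000 to 4,000 replicates per scenario (Monte Carlo SE about 0.004). Paired entries are M = 5 / M = 20.

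| f | ρ | Formula: SE ratio, type I | Averaged: SE ratio | Averaged: type I | Rubin's rules: type I |
|---|---|---|---|---|---|
| 10% | 0.3 | 0.934, 0.067 | 0.928 / 0.926 | 0.070 / 0.066 | 0.048 / 0.049 |
| 10% | 0.5 | 0.924, 0.070 | 0.920 / 0.920 | 0.070 / 0.076 | 0.050 / 0.054 |
| 10% | 0.7 | 0.914, 0.073 | 0.925 / 0.920 | 0.073 / 0.067 | 0.048 / 0.043 |
| 25% | 0.3 | 0.830, 0.104 | 0.827 / 0.823 | 0.105 / 0.109 | 0.048 / 0.053 |
| 25% | 0.5 | 0.806, 0.114 | 0.817 / 0.795 | 0.113 / 0.120 | 0.045 / 0.054 |
| 25% | 0.7 | 0.783, 0.125 | 0.780 / 0.777 | 0.131 / 0.132 | 0.048 / 0.054 |

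At 2% missing, the averaged analysis gave a type I error of 0.050 to 0.056. Further runs of the same design gave 0.057 to 0.077 at 10% and 0.092 to 0.131 at 25%. Rubin's rules use the same draws and hold the level, so averaging is the cause.

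**Effect sizes.** The SD of the contrast shrinks by 1 − √(reported variance). At ρ = 0.5 that is 1 − √0.925 = 3.8% at 10% missing and 1 − √0.8125 = 9.9% at 25%. A d standardised on that SD rises accordingly.

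**The case against.** Four points deserve weight.

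1. **Wording.** The sentence is garbled, and its reference to estimation might be a loose way of saying that estimates are averaged across imputations. That cannot be excluded. But the text attaches the averaging to each missing value, and even averaging estimates would leave the variance rule unstated. The sentence needs replacing on either reading.

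2. **The 25% figure.** All three sections that give a loss rate say 10%, and the gap between 220 and 165 is partly a separate sample-size inconsistency. Randomisation follows ADOS-2 confirmation (sections 5.4.1 and 7.3), so some of the gap could fall before randomisation. The only count of outstanding second visits is in section 7.3, Visit 4, Note-3: 25 children in March 2020. If the denominator is 220 and none returned, that is 25/220 = 11.4%, with a simulated type I error of 0.068 to 0.078. This point stands in part: 25% is conditional. However, section 12.2 itself expects repeated measures on only 165 of 220, and section 5.5.1 allows termination when electrodes are not tolerated, which can remove the primary outcome.

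3. **Size at the planned rate.** At 10% a nominal 5% test runs at about 6% to 8%. That is modest, but it is inflation of the primary test at the plan's own expected loss.

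4. **Reach.** Mediation is judged by a change in coefficient above 15%, the moderator models are exploratory, and the paired cost and quality tests are not said to use imputed data. The simulation used a continuous normal outcome, so it does not size the error for single-item ratings such as the Frankl Scale. These limits stand. The primary test and the Hypothesis 2 ANCOVAs remain affected.

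**Conclusion.** The concern holds. Followed as written, section 12.4 treats averaged imputations as observed data and gives anti-conservative inference for the primary endpoint. The direction follows from the method. The size depends on how much is missing: negligible at 2%, a type I error of about 7% at 10% missing (standard errors about 7% to 8% too small), and about 10% to 13% at 25% missing (standard errors roughly 17% to 22% too small). These figures assume normal outcomes, second visits missing completely at random and a correlation of 0.3 to 0.7. The formula and the simulation agree closely across that range. Because the defect lies in the primary confirmatory test, it should be corrected before the database is locked.

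**What to change.** Replace the imputation sentence in section 12.4 with a rule along these lines: each of M completed data sets (at least 20, fixed in advance) is analysed separately with the planned model, and the environment estimates and standard errors are combined by Rubin's rules. The pooled estimate is the mean of the M estimates. Its variance is the mean within-imputation variance plus (1 + 1/M) times the between-imputation variance. State the variables in the imputation model. The choice of 20 is a convention; the essential change is to pool after analysis and never average imputed values before it. Effect sizes should come from the same pooled analysis.

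Alternatively, drop imputation of outcomes and fit a likelihood-based linear mixed model to all observed visits. This is a larger change because it replaces the named ANCOVA, but it needs no pooling.

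The first option costs only wording and some programming, with no effect on participants or data collection. Whether SPSS v.22 pools this particular model automatically cannot be settled from the documents, but the two formulas can be applied to its output by hand. Confidence intervals will be slightly wider, as they should be.

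The plan should also state which loss, 10% or 25%, is expected among randomised children, since the extent of imputation depends on it.

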# 3.2 Study Outcome Measures

# 3.2.1 Outcome Measures for the Primary Objective

Our primary outcome measure is children's physiological response measured by EDA during the dental cleaning. EDA will be measured using the BIOPAC Systems, Inc. MP150 System. This physiological response is caused by sympathetic nervous system activation, which increases during stressful or painful situations. Sensors will be placed on the child's fingers and EDA recordings will be made immediately prior to and continuously throughout each cleaning. Two measures of tonic EDA will be collected: skin conductance level (SCL) and frequency of non-specific skin conductance responses (NS-SCR). See Table 1.

Table 1. Primary outcome measure of children's physiological responses for the SADE-2 Study.

Outcome measure (Completed by)	Measure & Description	Type of Measure (No. of Items)	When Administered	Specific Objective Tested	CRF Name (#)
Physiological Anxiety (Researcher- coded)	Electrodermal Activity (skin conductance level and frequency of non- specific responses) assesses level of sympathetic nervous system activation.	Psycho- physiological (N/A: scoring is continuous throughout recording)	Recorded at baseline and throughout both dental cleanings.	1	Scored EDA Form (23)

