### 12 STATISTICAL CONSIDERATIONS

# 12.1 Study Hypotheses

**Primary Objective:** To compare children's physiological anxiety (EDA - primary outcome) during the dental cleaning in SADE vs. RDE.

**Hypothesis 1:** Children will exhibit less physiological anxiety (SCL and NS-SCR frequency) during routine dental care in the SADE condition compared to the RDE.

**Secondary Objective 2:** To compare children's negative behavioral responses (behavioral distress, perception of pain, sensory discomfort - secondary outcomes) during dental cleanings in SADE vs. RDE.

**Hypothesis 2:** Children will exhibit fewer negative behavioral responses during routine dental care in the SADE condition compared to the RDE.

**Secondary Objective 3:** To test the degree to which physiological anxiety mediates the SADE intervention's effects on children's negative behavioral responses.

**Hypothesis 3:** Physiological anxiety mediates the effect of the intervention in decreasing child negative behavioral responses.

**Secondary Objective 4:** To test the degree to which specific child characteristics moderate the SADE intervention's effects on children's physiological and negative behavioral responses during dental cleaning.

**Hypothesis 4:** The magnitude of physiological and negative behavioral response change in the SADE, relative to the RDE, will be greater in children with ASD with increased sensory over-responsivity, high dental anxiety, greater ASD severity, lower IQ, and/or younger age.

**Secondary Objective 5:** To compare the SADE intervention to the RDE on quality of care, cost-effectiveness, and potential cost savings of dental cleaning.

**Hypothesis 5a:** The SADE intervention, compared to the RDE, is cost-effective and results in decreased overall costs.

**Hypothesis 5b:** The SADE intervention, compared to the RDE, results in improved quality of care as evidenced by thoroughness of dental cleaning.

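### The primary outcome, EDA, is recorded as two measures (SCL and NS-SCR frequency), and the plan does not say which measure, or whether either or both, decides Hypothesis 1.

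*Combined protocol and SAP*

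**What the plan says.** Section 3.2.1 treats EDA as the primary outcome and then gives it two components: "Two measures of tonic EDA will be collected: skin conductance level (SCL) and frequency of non-specific skin conductance responses (NS-SCR"). Neither is named as the deciding one. Hypothesis 1 in section 12.1 carries both: "Children will exhibit less physiological anxiety (SCL and NS-SCR frequency) during routine dental care in the SADE condition compared to the RDE".

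Section 12.4 tests the primary objective "using repeated measures ANCOVA for each outcome", and closes its general paragraphs with "Analyses will be performed using SPSS (v.22); a priori two-sided" 0.05. The mediation text in the same section keeps the measures apart, "then adding EDA estimates (SCL and NS-SCR) to models of dental environment difference on behavioral outcomes". The model for the primary objective does not: "Hypothesis 1 specifies an effect of environment on the outcome, thus the main effect of interest will be" B1, in one equation whose outcome is simply EDA.

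Section 12.2 gives a second significance level, "with 1-=0.80 and -=0.025 (Hyp 2"), with no sidedness. It states 220 recruited, 165 with repeated measures and a detectable d of 0.22, and says of attrition: "however the more conservative attrition estimate of 10% was used for these calculations". The pilot EDA effects are given as d = 0.44 to 0.46.

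The only multiplicity wording in 12.4 promises a judgement-based approach with effect sizes. It is attached to the mediation analysis and the secondary outcomes, not to Hypothesis 1.

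**The concern.** A primary claim needs a criterion fixed before the data are seen. Here there are two candidate results and no rule that turns them into a verdict on Hypothesis 1. If SCL favours the adapted environment and NS-SCR does not, the same data support the hypothesis when either measure suffices and fail it when both are needed. The choice could then be made after the results are known.

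The unexplained 0.025 adds to this. If it was meant as 0.05 divided between the two measures, a p value between 0.025 and 0.05 would pass under 12.4 and could fail under the intended split. If it was meant one-sided, or only for the secondary outcomes, it would not.

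**Working it through.** **Inputs.** Two primary measures (3.2.1, 12.1); two-sided 0.05 (12.4); 0.025 and power 0.80 (12.2); d = 0.22, 165 analysed, 220 recruited, 10% attrition (12.2; the Retention text in 5.3 repeats the last three). The correlation r between the two test statistics is not given and is varied as an assumption.

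**1. Reproduce the plan's 165.** For a within-child difference, n = ((z_alpha + z_power)/d)², then refined with the noncentral t.
- Two-sided 0.05: ((1.960 + 0.842)/0.22)² = 162.2, or 165 with the t distribution; power at 165 is 80.2%. This reproduces the plan.
- One-sided 0.025: same critical value, so again 165 and 80.2%.
- Two-sided 0.025: ((2.241 + 0.842)/0.22)² = 196.4, or 199 with the t distribution; power at 165 is 71.3%. This does not reproduce it.
- One-sided 0.05: 127.7, or 130. This does not reproduce it.

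**2. Attrition.** 220 × 0.90 = 198, whereas 165/220 = 0.75, a 25% loss. With 198 children and d = 0.22, power is 86.9% at two-sided 0.05 and 79.8% at two-sided 0.025.

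**3. Family-wise error if either measure suffices.** At r = 0 this is 1 − 0.95² = 9.75%. Otherwise it is the bivariate-normal probability that at least one |z| exceeds the critical value. The false-benefit column counts only results favouring the adapted environment.

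| Assumed r | Either at 0.05, two-sided | False-benefit part | Either at 0.025, two-sided |
|---|---|---|---|
| 0 | 9.75% | 4.9% | 4.9% |
| 0.5 | 9.1% | 4.5% | 4.6% |
| 0.7 | 8.3% | 4.2% | 4.3% |
| 0.9 | 7.0% | 3.5% | 3.6% |
| 0.95 | 6.5% | 3.2% | 3.3% |
| limit as r → 1 | 5% | 2.5% | 2.5% |

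If both are required at 0.05 each, the error cannot exceed 5%.

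**4. Power under each rule, 165 children, d = 0.22 on both measures, r from 0 to 0.9.**

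| Rule | Power |
|---|---|
| One named primary at 0.05 | 80.2% |
| Holm, per measure (normal approximation) | about 76-78% |
| Holm, at least one measure (normal approximation) | about 78-92% |
| One measure that must pass at 0.025 alone | 71.3% |
| Both required at 0.05 (simulated t pairs) | about 64-75% |

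Under Holm, higher r gives the lower figures; with both required, higher r gives the higher ones. At d = 0.44 to 0.46, power exceeds 99.9% under every rule.

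**The case against.** The strongest reply is that the plan already treats physiological anxiety as one outcome. In 12.4 the outcomes are listed as physiological anxiety and the negative behavioural responses, only one mediator is claimed, and Hypothesis 1 has one equation with one B1. On that view the phrase about each outcome does not establish one 0.05 test per EDA measure. This stands as far as it goes. But a single EDA variable is never constructed, so the equation cannot be fitted without a choice that the plan leaves open.

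A second reply is that Hypothesis 1 joins the measures with the word and. If that means both must succeed, error is not inflated. The words sit in a parenthesis explaining physiological anxiety, however, and no success criterion repeats them.

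A reader might also infer that 0.025 in 12.2 contradicts 0.05 in 12.4, or that it was a division of 0.05 that 12.4 forgot. The documents support neither. The 0.025 has no sidedness and sits beside a reference to Hypothesis 2. Read as one-sided, it equals two-sided 0.05 and reproduces the 165. The near fit of 198 to two-sided 0.025 is suggestive at most: 198 appears nowhere in the plan, which ties d = 0.22 to 165. Symbols in that sentence were lost in the text available, and Figure 1, with the estimates by measure, is not shown there. Neither is a fault of the plan, but the question stays open.

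Finally, at the pilot effects power is not at issue. That is true, but it shows only that a rule would cost little; it does not limit false positives.

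**Conclusion.** The missing decision rule for Hypothesis 1 is real and should be fixed. The error inflation is conditional: 5% to 9.75% two-sided, with a false-benefit part of at most 4.9% against 2.5% for one test. It arises only if each measure is tested at 0.05 and either is allowed to suffice. These figures assume jointly normal statistics with non-negative correlation. The 9.75% needs zero correlation, which is the extreme case for two tonic measures from one recording. It would go too far to say that the plan commits to that reading.

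The 0.025 is a level whose sidedness and purpose are missing, not a demonstrated contradiction. The attrition arithmetic is a separate inconsistency: a 10% loss from 220 leaves 198, while 165 implies a 25% loss.

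**What to change.** Before database lock, state one primary decision rule in 12.4. Any of these closes the gap:

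- **(a) Holm across SCL and NS-SCR at overall two-sided 0.05:** the smaller p value against 0.025, then the other against 0.05. Hypothesis 1 is met if at least one measure passes in the direction of less anxiety under SADE, and the claim is limited to the measure or measures that pass.
- **(b) One named primary measure at two-sided 0.05,** with the other secondary.
- **(c) Both measures required, each at two-sided 0.05,** if that was the intended meaning of Hypothesis 1.

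In 12.2, state the sidedness and purpose of the 0.025 so that it agrees with 12.4. Reconcile 220, 10% and 165, and restate the power or detectable effect under the chosen rule. Section 7.3 (Visit 4, Note-3) says recruitment is complete, so this is a restatement and not a reason to enrol more.

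This is a cheap improvement: a few sentences, with no new data. The price in power is the second table in the working, and it matters only if the true effect is near 0.22. Option (b) loses no power but makes the other measure secondary; option (a) costs a few percentage points per measure; option (c) costs the most.

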#### 5.4 Treatment Assignment Procedures

# 5.4.1 Randomization Procedures (if applicable)

Following confirmation of ASD diagnosis (administration of ADOS-2), participants will be randomly assigned to the order of treatment, receiving either the Regular Dental Environment (RDE) condition or Sensory Adapted Dental Environment (SADE) condition for their first cleaning. Because we anticipate different rates of participation between gender and age, randomization will be stratified by gender and age (6.0-9.5 years and 9.6-12.11 years) so there is a balance in order of treatment between boys and girls and younger and older children in each order of environment. Randomization will be performed by our PhD biostatistician following a blocked randomization schema for each of the gender-age stratum. We anticipate that the largest stratum will be younger boys (~56% of the sample), followed by older boys (24%), younger girls (15%), and older girls (6%), thus block sizes will vary so that the study team cannot anticipate what the first treatment for a participant will be.

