## Secondary Objective 4: Hypotheses 4a & 4b

Hypothesis 4 seeks to determine whether there is a moderating effect of EDA and negative behavior variables on the impact of the environment. It is anticipated that there is greater benefit of the SADE intervention for ASD children with greater ASD severity, decreased IQ, increased sensory over-responsivity, higher dental anxiety, and/or younger age. These models are exploratory and will be assessed initial with each moderator alone. Then a stepwise regression model will be built to see if there are moderators that are more important than others. The previously described associations will assist us in determining if there is a risk of collinearity amongst the variables.

Hyp 4: EDA or Negative behavior =  $B_0$  +  $B_1$ \*Environment + B2\*Moderators + B3\*(Environment\*Moderators) + Covariates

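### Section 12.4 adjusts for randomised order but states no visit (period) or environment-by-order term and no covariate coding: a free improvement for a two-visit crossover

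*Combined protocol and SAP*

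**What the plan says.** Section 12.4 tests the primary objective by "examining the within-subject factor of dental environment (SADE vs RDE) using repeated measures ANCOVA for each outcome". The a priori "covariates include age (continuous), randomized order of visit, gender, and temperature". Under Primary Objective: Hypothesis 1 it adds: "Hypothesis 1 specifies an effect of environment on the outcome, thus the main effect of interest will be" B1, in a model with an intercept, B1*Environment and covariates. The Hypothesis 2 equation for the behavioural outcomes has the same form.

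Section 12 contains no visit, period or environment-by-order term. The only interaction written out is Environment*Moderators for Hypothesis 4, and those moderators are child characteristics, not order. SPSS is named, but no procedure and no covariate coding.

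Section 5.4.1 randomises order in blocks within gender-age strata. Section 6.2 puts the two cleanings about four to six months apart. On size, section 12.2 says: "This N will allow for the detection of a within group change attributable to environment of Cohen's d = 0.22".

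**The concern.** In a two-visit crossover, each child's SADE-minus-RDE difference contains the environment effect plus or minus any change from the first to the second visit, with the sign set by order. Such a change is plausible here. The child has already been through the study procedure once, section 7.6 allows cavities found at Visit 3 to be treated before Visit 4, and section 8.1 says the video coder, who cannot be blinded, changes yearly.

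An order main effect is constant within a child, so in complete pairs it cancels out of the difference and cannot remove this change. Only a visit term, or equivalently environment-by-order, does so. What is at stake is power near the effect the trial is sized for and for the small distress-behaviour effects. In some fits of the named method, the meaning of B1 and the validity of its test are also at stake, and the plan does not say which fit is intended.

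**Working it through.** **Inputs from the documents.** 165 complete pairs; detectable d = 0.22; power 0.80; pilot EDA effects 0.44-0.46; pilot distress-behaviour effects 0.11-0.23 (all section 12.2); two-sided 0.05 (section 12.4); gender-age strata of about 56%, 24%, 15% and 6% (section 5.4.1).

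**Assumed.** 1:1 order allocation; visit shifts s of 0.22, 0.3 and 0.5 SD of the within-child difference; all d values in that same SD; ages uniform within strata.

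**The plan's own figure.** d = (1.960 + 0.842)/sqrt(165) = 0.218, or 0.219 with the t distribution. Power at d = 0.22 is 0.802. So 0.22 reproduces at two-sided 0.05. Section 12.2 also mentions 0.025; read as two-sided, that would give power 0.713.

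**Additive fit, near-equal orders.** Write D = d + s*g + e, with g = +1 or -1 by order and SD(e) = 1. With g balanced, the true variance of the mean is 1/N, but the estimated variance is about (1 + s^2)/N. Type I error is then about P(|Z| > 1.96*sqrt(1 + s^2)):
- s = 0.22: 1.96*sqrt(1.0484) = 2.007, giving 0.045
- s = 0.3: 1.96*sqrt(1.09) = 2.046, giving 0.041
- s = 0.5: 1.96*sqrt(1.25) = 2.191, giving 0.028

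The exact calculation uses a noncentral chi-square for the variance. The ranges below reflect which order holds the odd child (83:82 or 82:83):

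| s | Type I | Power, d = 0.11 | Power, d = 0.22 | Power, d = 0.23 | Detectable d |
|---|---|---|---|---|---|
| 0 | 0.050 | 0.290 | 0.802 | 0.836 | 0.219 |
| 0.22 | 0.045 | 0.268-0.280 | 0.784-0.794 | 0.819-0.828 | 0.222-0.224 |
| 0.3 | 0.041 | 0.253-0.268 | 0.770-0.784 | 0.807-0.819 | 0.224-0.228 |
| 0.5 | 0.029 | 0.205-0.227 | 0.718-0.744 | 0.760-0.783 | 0.235-0.241 |

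At d = 0.44, power stays above 0.999. Simulation agrees, and with a visit term power at d = 0.22 is 0.801-0.803 at every s.

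Random-intercept fits at s = 0.3 show the mechanism. The mean standard error of B1 is 0.0813 with environment alone, 0.0813 after adding order, age and gender, and 0.0779 once visit is added. The ratio is as expected: 0.0779*sqrt(1.09) = 0.0813.

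**A different N.** The Retention text says: "We have allowed for a loss of 10%, targeting a sample of 165 participants with complete data from a recruited sample of 220 children". But 165/220 is a 25% loss; a 10% loss leaves 198. At 198, power at d = 0.22 is 0.869 with no shift, then 0.858, 0.849 and 0.813.

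**Additive fit, unequal orders.** At 92:73 the mean of g is 19/165 = 0.115, so the bias is 0.115*s, or 0.058 at s = 0.5. Type I error is then about 0.076. At 87:78 the test is still conservative (0.038 at s = 0.5).

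**Crossed fit** (covariates interact with environment):
- *Order as a balanced factor:* the shift is removed. Simulated type I error is about 0.05 and power at d = 0.22 about 0.80.
- *Order as an uncentred 0/1 covariate:* B1 is the mean difference in one sequence of about 82 children, with standard error 1/sqrt(82) = 0.110. Under the null at s = 0.22 the test statistic is centred at 0.22/0.110 = 2.0, so it rejects about half the time. Simulated type I error is about 0.50 at 0.22 SD and 0.77 at 0.3 SD.
- *Age uncentred:* B1 refers to age zero. With the strata rescaled to sum to 100%, mean age is about 8.8 and its SD about 1.9. The standard error is about 0.078*sqrt(1 + (8.8/1.9)^2) = 0.37. Simulation gives 0.374-0.378 against 0.078, about 4.8 times, with power 0.09 at d = 0.22 and about 0.21 at d = 0.44.
- *Age centred, gender a crossed factor:* B1 refers to the unweighted boy/girl mean. The standard error is 0.097 and power at d = 0.22 is 0.62.
- *Age and gender both centred, order balanced:* the standard error is 0.078 and power 0.801.

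Temperature is not in the crossed-fit simulations, because the documents give no distribution for it.

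**The case against.** The strongest reply is that a repeated measures ANCOVA in its multivariate form already crosses between-child terms with the within-child factor. Environment-by-order would then be present without being named, and the equations in 12.4 could be schematic. This is fair as far as it goes, and it means the additive fit cannot be called the only reading. It does not close the point: crossing removes the visit change only if order enters as a balanced factor. The plan lists order among covariates and gives no coding, and the uncentred 0/1 version is worse than the additive fit.

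The wording about order might also be meant as first versus second visit, which is the missing term. The later sentence in 12.4 on characteristics unbalanced between orders points to sequence instead, so this is possible but weaker.

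The size is also open to challenge. The visit shift is assumed, detectable d moves only to 0.228 at most for shifts up to 0.3 SD, and the primary outcome was planned on pilot effects where nothing is lost. At d = 0.11 power is low with or without the term. Section 12.2 does not say that the pilot effects are in within-child SDs. All of this stands, and it keeps the point modest under the additive reading.

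**Conclusion.** The point holds as a free improvement. As its equations are written, 12.4 leaves any first-to-second-visit change in the error. With near-equal orders among completers this makes the environment test mildly conservative, and it costs power near d = 0.22 and for distress behaviour, not at the pilot EDA effect. The figures rest on the assumed shifts of 0.22-0.5 SD.

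Three stronger readings are tempting, and the documents do not support them:
- *The planned primary test is conservative whatever happens.* That holds only for the additive fit with near-equal orders. At 92:73 it fails, though blocking makes such a split unlikely. The averaging of imputed values in 12.4 also pushes the other way: with 10% of second visits missing, an assumed within-child correlation of 0.6 and no visit change, simulated type I error was about 0.07.
- *Crossing the covariates always absorbs the shift.* It does so only with balanced coding of order.
- *The primary analysis is invalid or badly underpowered.* The severe figures (type I error 0.50, power 0.09) each need a crossed fit with a particular uncentred coding that the plan does not state. They show why the coding should be fixed in advance, not what the trial will do.

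**What to change.** State in 12.4, before database lock, that visit number (equivalently environment-by-order) is in the within-child model for the primary and behavioural outcomes.

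- **Preferred:** a mixed model with one row per visit, a random intercept for child, and main effects Environment + Visit + Order + Age + Gender + Temperature, using visit-level temperature if it is recorded at each visit.
- **If repeated measures ANCOVA is kept:** enter order as a between-subject factor with balanced (+1/-1) coding, crossed with environment, and mean-centre every other covariate (age, gender as a numeric term, temperature), so that the environment test is the average effect.

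In either case, carry visit and order in the imputation model.

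The cost is about one residual degree of freedom, no new data, and a rewording of 12.4 and its imputation step. If there is no visit change at all, power at d = 0.22 goes from 0.8022 to 0.8021.
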